7.2.1. Reproductive Restrictions

Verinurad is not genotoxic, has no effect on fertility in animal studies, and carries a low risk for foetal harm at maternally nontoxic doses in animal studies.

A female subject who participates in the clinical trial must either:

- Be of non-childbearing potential, that is, she must be surgically sterilized or post-menopausal as described in Section 7.2.1.1, OR

- If of childbearing potential, must be using highly effective methods of birth control as described in Section 7.2.1.2.

7.2.1.1. Women of Non-Childbearing Potential

Women of non-childbearing potential are defined as female subjects who are permanently surgically sterilized or post-menopausal.

Acceptable methods of sterilization include:

- Surgical bilateral oophorectomy (with or without hysterectomy) at least 6 weeks before Screening. In the case of oophorectomy alone, only when the reproductive status of the woman has been confirmed by follow-up hormone level assessment.
- Hysterectomy at least 6 weeks before Screening.
- Bilateral salpingectomy.

Females are considered post-menopausal if they have had amenorrhea for at least 12 months or more following cessation of all exogenous hormonal treatments and FSH levels are in the post-menopausal range (eg, age appropriate, history of vasomotor symptoms) or for women <60 years the FSH levels are >40 mIU/mL.

7.2.1.2. Women of Childbearing Potential

A woman is considered of childbearing potential, ie, fertile, following menarche and until becoming post-menopausal, unless permanently sterile. Women of childbearing potential who are sexually active must agree to use, with their partner, an approved method of highly effective contraception from the time of IMP administration until 3 months after the Follow-up Visit.

- A barrier method must be used in combination with one of the following methods, considered to be highly effective (failure rate <1% per year when used consistently and correctly):
 - Hormonal contraception, ie, combined oral contraceptives, injectable¹ or implantable¹ hormonal contraceptives,
 - Hormonal or non-hormonal intrauterine device¹ (IUD, loop), established IUD¹ or intrauterine system (Note: The IUD must have a failure rate <1%),
 - Surgical sterilization¹ (ie, bilateral tubal ligation for females; vasectomy for male partners [must have been vasectomized before the female subject entered the clinical trial and he is the sole sexual partner of the female subject during the clinical trial]).
- Barrier methods of contraception include:
 - Condom (**without** spermicidal foam/gel/film/cream/suppository or fat- or oil-containing lubricants)
 - Occlusive cap (diaphragm or cervical/vault caps) **with** spermicidal gel/film/cream/suppository

¹ These methods are considered to have low user dependency.

Note: Double-barrier is not considered a highly effective method.

Female subjects must agree not to attempt to become pregnant, must not donate ova and must not breastfeed starting at Screening and throughout the clinical study and for 90 days after receiving the Follow-up Visit.

Women should be informed of the potential risks associated with becoming pregnant while enrolled.

Alternatively, true abstinence is acceptable when it is in line with the subject's preferred and usual lifestyle. Periodic abstinence (eg, calendar, ovulation, symptothermal, post-ovulation methods), declaration of abstinence for the duration of a trial and withdrawal are not acceptable methods of contraception.

Pregnancy Testing

Women of childbearing potential can be included only after a negative highly sensitive serum pregnancy test. Additionally, urine pregnancy testing will be done as per the Schedule of Assessments.

Pregnancy

If the subject becomes pregnant during the study this should be reported to the Investigator. The Investigator should also be notified of pregnancy occurring during the study but confirmed after completion of the study. The pregnancy will be followed and the status of mother and child will be reported to the Sponsor after delivery.

A pregnancy notification form and follow-up will be completed.

7.2.1.3. Male Subjects

Verinurad had no effects on fertility or embryo-foetal development in rats at doses up to 300 mg/kg/day and did not affect embryo-foetal development in rabbits at doses up to 30 mg/kg/day. There is inadequate evidence of safety of allopurinol in human pregnancy, although it has been in wide use for many years without apparent ill consequence.

Male subjects participating in this study are not required to apply contraception. However, it is recommended that male subjects should not donate sperm until at least 3 months after the Follow-up Visit. In addition, as a precaution, all male subjects should avoid fathering a child AND exposing a foetus to verinurad by either true abstinence or use of a highly effective method of contraception (see definition above), together with their female partner, starting from the time of IMP administration until at least 3 months after the Follow-up Visit.

Pregnancy

Male subjects will be instructed that, if their partner becomes pregnant during the study, this should be reported to the Investigator. The Investigator should also be notified of pregnancy occurring during the study but confirmed after completion of the study. In the event that a subject's partner is subsequently found to be pregnant after the volunteer is included in the study, then consent will be sought from the partner and, if granted, any pregnancy will be followed and the status of mother and/or child will be reported to the Sponsor after delivery.

A pregnancy notification form and follow-up will be completed.

7.3. Replacement of Subjects

Subjects who are withdrawn from the study due to AEs or changes in safety parameters will not be replaced unless a specific sample size is to be met for statistical purposes and if the Sponsor's responsible physician and the Investigator agree it is safe to do so. Subjects who withdraw or are withdrawn from the study for suspected or confirmed COVID-19 infection or other reasons may be replaced following discussion with the Sponsor.

8. STUDY STOPPING RULES

8.1. Discontinuation of Investigational Medicinal Product and Withdrawal from the Study

Subjects must be discontinued from treatment in the following situations:

- Subject decision. The subject is at any time free to discontinue treatment, without prejudice to further treatment.
- Severe noncompliance to study protocol.
- Any significant and clinically relevant changes in the safety parameters (eg, ECG, blood pressure, pulse rate, body temperature, laboratory assessments and AE) making the continuation of IMP administration unjustified.
- Study-specific withdrawal criteria: If a subject reports any event/symptoms that are considered unacceptable by the subject or the Investigator, he/she will be withdrawn from the study. In particular:
 - Any severe or serious AE that is judged as possibly related to the IMP by the Investigator.
 - Any case of Potential Hy's Law (PHL) according to [Appendix C](#).
 - QTc prolongation defined as QTcF >500 ms, or a prolongation from baseline of >60 ms, confirmed (persistent for at least 5 minutes) and determined post-dose either during continuous 12-lead safety ECG monitoring or on a repeat 12-lead safety ECG.
 - See [Appendix D](#) for details on the handling of renal-related or urolithiasis treatment-emergent AEs, and the handling of serum creatinine elevation, which includes criteria for stopping treatment.
 - Pregnancy.
 - Any confirmed COVID-19 case that warrants discontinuation in the judgment of the Investigator or Sponsor to protect the safety of the subject, other study participants or study site staff.

The appropriate AE form in the case report form (CRF) is to be completed.

8.1.1. Premature Termination of the Study and Stopping Criteria

The study will be put on temporary hold (defined as treatment stopped for enrolled subjects and stop enrolment of subjects into the study) pending further safety data analysis if any of the following criteria occur in subjects receiving IMP:

- A “serious” adverse reaction (ie, an SAE considered at least possibly related to IMP administration as per guideline EMEA/CHMP/SWP/28367/07 Rev. 1 [[22](#)]) in 1 subject;
- “Severe” non-serious adverse reactions (ie, severe non-serious AEs considered as at least possibly related to the IMP administration) in 2 subjects in the same treatment sequence, independent of within or not within the same System Organ Class (SOC).

The study will be terminated prematurely if:

- The Investigator and the Sponsor assess that the number and/or severity of AEs justify discontinuation of the study. For instance, when there is at least 1 case of fatal SAE or 2 cases of other SAEs, in both situations considered related to the IMP by the Investigator and the Sponsor.
- The Sponsor considers the applied doses of the IMPs to be no longer relevant.
- The Sponsor decides to discontinue the study.
- Data, that were not known before, become available and raise concern about the safety of IMP so that continuation would pose potential risks to the subjects.
- New data become available regarding COVID-19, which raise concern for the safe study conduct so that continuation would pose potential risks to the subjects or the study site staff.

Premature termination of the study must be mutually agreed upon by the Investigator and the Sponsor and must be documented. However, study results will be reported according to the requirements outlined in this CSP as far as applicable.

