5.3.2. Overall Study Design

This study will be a single-centre, randomised, placebo-controlled, double-blind, 3-period, cross-over Phase I study to assess the effect on the QTcF interval of a single oral dose of verinurad 24 mg ER8 formulation (therapeutic exposure) or verinurad 40 mg IR formulation (supra-therapeutic exposure), each in combination with allopurinol 300 mg, compared to placebo in healthy subjects.

There are 3 study treatments (see also [Table 9-3](#)):

- Treatment A: Verinurad 24 mg ER8 formulation co-administered with 300 mg allopurinol
- Treatment B: Verinurad 40 mg IR formulation co-administered with 300 mg allopurinol
- Treatment C: Matched placebos for both verinurad and allopurinol

All subjects will receive a single dose of all 3 treatments (A, B, and C) in a cross-over design with wash-out periods of at least 7 days between each study dose administration. Subjects will be randomised to the treatment sequence (ABC, BCA, CAB, etc.) using

William's Latin square. The treatments will be administered in a double-blind manner after an overnight fast of at least 10 hours.

There will be 5 visits to the study centre, including 3 visits that are residential. The study will comprise the following periods and visits:

- A Screening Period of maximum 28 days (Visit 1);
- Three treatment periods of 3 days each, during which subjects will be resident at the study centre from the morning of the day before administration of the study dose (check-in, Day -1) until discharge 2 days after study dose administration (check-out, Day 3; Visits 2 to 4);
- Wash-out periods of at least 7 days between each study dose administration;
- A final visit within 7 to 10 days after the last study dose administration (Follow-up Visit; Visit 5).

A total of 24 subjects are planned to be randomised to achieve at least 20 evaluable subjects.

The study design is deemed appropriate for conduct in healthy volunteers during COVID-19 pandemic.

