9.9.2. Procedures for Randomisation

Upon completion of the randomisation requirements specifications form, randomisation will be produced by Parexel according to the AstraZeneca randomisation system (AZRand).

Subjects will be randomised according to a randomised William's Latin square to receive the 3 study treatments (Treatment A: verinurad 24 mg ER8 + allopurinol; Treatment B: verinurad 40 mg IR + allopurinol, Treatment C: placebo) in 1 of 6 treatment sequences: ABC, BCA, CAB, ACB, BAC, or CBA.

The randomisation will be completed using consecutive randomisation codes.

The number of subject identifiers generated for the study will account for the number of randomised subjects per the sample size calculation (N=24; see Section 12.4) as well as providing sufficient randomisation numbers for replacements. For this study, a total of 48 subject identifiers will be randomly assigned to the treatment sequences (ABC, BCA, CAB, ACB, BAC, CBA).

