9.10. Blinding

9.11. Methods for Ensuring Blinding

This study is double-blind with regard to IMP (verinurad and allopurinol or the matching placebos).

Placebos will be matched with their respective test product (verinurad or allopurinol) for formulation, appearance, and amount.

Any clinical staff involved in the preparation or administration of the IMP and who become unblinded will take no further part in the study.

The randomisation list should be kept in a secure location until the database is locked or equivalently, a clean file is declared.

The pharmacokineticist will remain blinded during the study conduct, unless otherwise required, based on study findings.

The pharmacokineticist will be unblinded to perform the final PK analyses after all subjects have completed the study, final bioanalytical results are available and all required study data are considered clean. This may occur prior to database lock.

The following personnel will have access to the randomisation list:

- The AstraZeneca personnel carrying out the labeling and packaging of subject-specific treatments

- The pharmacy personnel preparing IMP at the site
- The personnel performing the bioanalyses of the plasma/urine samples.

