12.4. Determination of Sample Size

Study sample size for a concentration-QTcF (C-QTcF)-based interval analysis is based on the recommendation from Garnett et al 2018 [21] to have 16 to 32 subjects on drug and 8 to 16 subjects on placebo. The type-1 error rate has been shown to be controlled at around 5% when the true effect is 10 ms in small-sized studies of 6 to 12 subjects with multiple measurements per subject.

A 3-period cross-over study, using C-QTcF-based interval analysis, with 2 verinurad doses and placebo in 20 evaluable healthy volunteers is expected to exceed the recommendations proposed in Garnett et al 2018 [21].

Twenty-four subjects will be randomised to a 6-sequence William's design for 3 periods and 3 treatments to achieve 20 evaluable subjects based on an expected dropout of 17%.

Evaluable subjects are defined as subjects for whom baseline and post-baseline QTcF results from smoothed dECG data are available for at least 2 treatment periods (where 1 of

the treatment periods needs to be the period in which the subject received placebo), and who have no major protocol deviation thought to impact on the analysis of the dECG data.

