12.12.2. Adverse Events

All AEs will be coded using MedDRA vocabulary and will be listed for each subject. Adverse events will be assigned to a treatment based on the start date/time of the AE in relation to dosing in that period; for tabulation purposes the AE will then be assigned to the treatment received in the respective treatment period as follows:

- Screening: all AEs with start date/time prior to dosing in Treatment Period 1 (from time of randomisation for AEs and from time of signed ICF for SAEs).
- Treatment Period 1: AEs with start date/time at the time of or after dosing in Treatment Period 1 until the time of dosing in Treatment Period 2.
- Treatment Period 2: AEs with start date/time at the time of or after dosing in Treatment Period 2 until the time of dosing in Treatment Period 3.
- Treatment Period 3: AEs with start date/time at the time of or after dosing in Treatment Period 3 until the final Follow-up Visit.

Adverse events with missing start dates/times will be handled as follows:

- If the start date is completely missing but the end date is known and shows that the AE ended on or after the first dose date, then the start date will be imputed as the first day of dosing; if the end date is known and shows that the AE ended before the first dose date, then the screening date will be used for the start date. If the end date is non-informative (ie, is missing or does not contain enough information), the start date will be imputed as the first date of dosing;
- If only the start day is missing the day will be imputed as the first day on which a dose was given in that month unless the end date is known and shows that the AE ended before a dose was given in that month; in which case the date will be imputed as 01. If the end date is non-informative (ie, is missing or does not contain enough information), the start date will be imputed as the first date of dosing in the known month. If the month is not a dosing month the date will be imputed as 01;

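### The hold for severe non-serious related reactions counts within a treatment sequence, so two such reactions to the same treatment usually do not trigger it

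*Combined protocol and SAP*

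**What the plan says.** Section 8.1.1 sets two triggers for a temporary hold. One serious related reaction in any subject is enough. Severe non-serious related reactions are counted "in 2 subjects in the same treatment sequence, independent of within or not within the same System Organ Class (SOC"). A hold means "treatment stopped for enrolled subjects and stop enrolment of subjects into the study".

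Section 5.3.2 states "All subjects will receive a single dose of all 3 treatments (A, B, and C) in a cross-over design", and Section 9.9.2 randomises subjects "in 1 of 6 treatment sequences: ABC, BCA, CAB, ACB, BAC, or CBA". For reporting, Section 12.12.2 uses a different unit: "Adverse events will be assigned to a treatment based on the start date/time of the AE in relation to dosing in that period".

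Section 8.1 withdraws the individual subject after "Any severe or serious AE that is judged as possibly related to the IMP by the Investigator". Section 8.1.1 also lets the Investigator and Sponsor end the study on the number or severity of AEs. No section redefines treatment sequence or corrects the unit in the hold criterion.

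**The concern.** A count-based safety trigger should group events that may share a cause. Here the grouping is the order of dosing. Each treatment is given in two sequences in every period: B goes to BCA and BAC in Period 1, ABC and CBA in Period 2, and CAB and ACB in Period 3. Subjects who receive the same drug and dose in the same period are thus split between two counts, and over the whole study between six.

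The unit errs in both directions. It misses two Period 1 reactions to B when one subject is in BCA and the other in BAC, although neither has had any earlier study dose. It fires on a reaction to B in Period 1 and a reaction to placebo in Period 2 when both subjects are in BCA. At the limit, six subjects, one per sequence, could react severely to 40 mg IR without meeting the criterion.

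What is at stake is the dosing of remaining subjects after a second severe related reaction to one treatment. Section 5.4 puts the Cmax of 40 mg IR at 10 times worst-case clinical exposure, and the documents give no severe-AE rate for that dose.

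**Working it through.** **Inputs.** 24 subjects, 6 sequences and 3 periods (Sections 9.9.2 and 12.4). Equal allocation gives 24/6 = 4 per sequence; the design implies this but the plan does not state it. The plan's own sample-size figure is consistent: 24 randomised for 20 evaluable is a loss of 4/24 = 16.7%, given as 17%. The plan gives no operating characteristics for the hold rule, so there is no figure of that kind to reproduce.

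**Conditional miss rate.** Suppose exactly two subjects react to the same treatment, and every exposed subject is equally likely to be affected. With s sequences having received that treatment, 4 subjects each:

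P(different sequences) = C(s,2) × 16 / C(4s,2)

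| Both reactions in | s | Missed pairs / all pairs | Miss rate |
|---|---|---|---|
| Period 1 | 2 | 16/28 | 57% |
| Periods 1-2 | 4 | 96/120 | 80% |
| Periods 1-3 | 6 | 240/276 | 87% |

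The figures are the same for A, B and C. With 3 to 8 subjects per sequence they range over 53-60%, 77-82% and 85-88%. If each reactor's sequence is drawn independently (1 − 1/s), they are 50%, 75% and 83%. Of the 276 whole-study pairs, 276 − 120 = 156 include a Period 3 reaction, when a hold may protect few remaining doses. The first two rows are therefore the relevant ones.

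**How often this might arise.** Section 5.2.1.4 reports 2 AEs above Grade 2 among 293 pooled Phase I subjects. The grading scale differs and relatedness is not stated, so this is only a rough guide. With p = 2/293 = 0.0068 per subject:

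- Present rule: 1 − [P(Bin(4,p) ≤ 1)]^6 = 0.0017, about 0.2% of trials.
- Same-treatment rule, by simulation: about 0.4% with equal risk on A, B and C; about 0.6% with risk on A and B only.
- Any 2 subjects: P(Bin(24,p) ≥ 2) = 0.0116, about 1.2%.
- Active treatment (A or B): about 1.2% if all risk is on A and B, since it then equals the any-2 rule. With equal risk, the active share is 2/3 × 0.0068 = 0.0046 and P(Bin(24, 0.0046) ≥ 2) is about 0.5%.

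**If experience with 40 mg IR proves worse.** At an assumed 5% rate on one treatment only, the chance of a hold over the study is 1 − [P(Bin(4, 0.05) ≤ 1)]^6 = 8.1% counted by sequence and P(Bin(24, 0.05) ≥ 2) = 33.9% counted by treatment. At 10% it is 27.6% against 70.8%.

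**Cost in extra holds.** Assume a background risk q per dose, equal on A, B and C. The per-subject risk is 1 − (1−q)^3 over all doses and 1 − (1−q)^2 over the two active doses.

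| q per dose | Present rule | Same treatment | Active, any sequence | Any 2 subjects |
|---|---|---|---|---|
| 0.5% | 0.8% | 1.9% | 2.4% | 5.0% |
| 1% | 3.0% | 6.9% | 8.2% | 15.9% |

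The active column is P(Bin(24, 0.009975) ≥ 2) and P(Bin(24, 0.0199) ≥ 2). Allowing for subjects withdrawn after a placebo reaction lowers the second to 8.1%. The same-treatment column is simulated with withdrawal after the first reaction.

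**The case against.** The strongest case for leaving the text alone has four parts.

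1. **Rarity.** One of the two events in the pooled data was a tooth infection, the combination study reported only mild AEs on treatment, and at 2/293 every version of the rule triggers in about 1.2% of trials or fewer. This stands as a limit on importance. It does not justify the unit, because a stopping rule is written for the case where prior experience misleads.
2. **Other safeguards.** One related SAE triggers a hold, each affected subject is withdrawn, and the Investigator and Sponsor can stop on judgment. These limit the harm. They cover serious events, one subject, or discretion; none is an automatic count for severe non-serious reactions.
3. **The obvious repair has a gap.** Counting after the same treatment would drop a reaction on A plus one on B in one sequence, which triggers a hold now, although A and B contain the same two drugs (Table 9-3). With 1% risk per dose on A and B only, about a third of present triggers would be lost. This stands, and the fix below is worded to avoid it.
4. **Blinding.** Counting by treatment needs the code, but so does counting by sequence.

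A reader might infer that the rule fails 87% of the time. The documents do not support that: the figure is conditional on two reactions to one treatment and includes Period 3. A reader might also infer that the unit is meaningless. It is not, since subjects in one sequence share current treatment and dosing history; it is too narrow. Nor are all mixed-treatment pairs false alarms. With equal risk, two-thirds of two-subject triggers follow different treatments, but about a third of those are A plus B.

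**Conclusion.** The criterion is wrong as written and should be corrected. Given two subjects reacting to the same treatment, the automatic hold is missed more often than not while later doses are still due: 57% for Period 1 and 80% for Periods 1-2. This rests on risk unrelated to sequence and 4 subjects per sequence, and it changes little with the number per sequence. The absolute probability of needing the rule is probably small and cannot be fixed from the documents for 40 mg IR.

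Two further inferences go too far. Subjects are not left without protection, given the serious-reaction hold, individual withdrawal and discretionary termination. The primary QTcF analysis is not undermined, since its method does not depend on this rule. The phrase may be a slip for treatment, but nothing in the documents says so, and it remains the operative rule.

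**What to change.** In Section 8.1.1, replace the restriction to one treatment sequence with *in 2 subjects after active treatment (A or B), regardless of treatment sequence*, and keep the clause on SOC. Name someone who already has the randomisation list to make the count and report only whether the criterion is met. Section 9.11 already lists "The pharmacy personnel preparing IMP at the site". This wording keeps every active-active pair that triggers now and adds those split across sequences. It no longer counts reactions on placebo.

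If no unblinded count is wanted, use *in 2 subjects, regardless of treatment sequence*, and accept the larger number of holds.

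The cost is an amendment of one phrase, a named person, and more temporary holds, as tabulated above. A hold could also cost evaluable periods: "Evaluable subjects are defined as subjects for whom baseline and post-baseline QTcF results from smoothed dECG data are available" for at least two periods, one of them placebo (Section 12.4). Sample size and the primary analysis method stay as they are.
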